#### **12.5 Secondary Analyses**

*Analysis of Secondary and Tertiary Outcomes.*

We will conduct unadjusted analysis examining the treatment effect of endotracheal tube securement method on each of the pre-specified secondary and tertiary outcomes. Continuous outcomes will be compared with the Mann-Whitney U test and categorical variables with the Chi-square or Fisher Exact testing as appropriate.

*Subgroup Analyses.*

We will conduct unadjusted analysis examining the treatment effect of endotracheal tube securement technique on incidence of lip ulcers, tube dislodgement, and VAP in each of the pre-specified subgroups. Data will be presented as odds ratios and 95% confidence intervals for categorical variables and as mean differences and 95% confidence intervals for continuous variables.

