## **12.0 Statistical Considerations**

### **12.1 Sample Size Determination**

We estimated the incidences of tube dislodgement to be 20 per 1000 ventilator days and the incidence of lip ulcer development in the previous 12 months was 1.1 per 1000 ventilator days. Using the sum of these overall incidences of 21.1 per 1000 ventilator days and a standard deviation of 15 per 1000 ventilator days, we calculated a need for 142 patients in each arm to detect a clinically meaningful change of 5 episodes per 1000 ventilator days with 80% power at a two-sided alpha level of 0.05. We plan to enroll 500 patients which would allow for a 5.6% dropout or loss to follow-up rate. We used PS software to calculate the sample size.

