### **12.2 Statistical Analysis**

#### **Analysis principles**

- Primary analysis will be conducted on an intention-to-treat basis (patients with protocol violations are analyzed per the assigned treatment arm).
- All hypothesis tests will be two sided, with an  $\alpha$  of 0.05 unless otherwise specified.
- All analyses will be unadjusted unless otherwise specified.
- Subgroup analyses will be performed irrespective of treatment efficacy.

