#### **12.6 Presentation of Statistics**

Continuous variables will be described as mean and standard deviation or median and 25th percentile – 75th percentile or bootstrapped 95% confidence intervals as appropriate. Categorical variables will be given as percentage and number. All between-group comparisons with continuous variables will be performed using Mann-Whitney U tests and Chi-square or Fisher's exact test for categorical variables

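### Section 12.5 estimates the treatment effect separately within each unnamed subgroup and adds no interaction test, so it cannot show whether the effect differs between subgroups

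*Combined protocol and SAP*

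**What the plan says.** The subgroup paragraph of section 12.5 plans an unadjusted analysis of the effect of securement method on tube dislodgement, lip ulcers and VAP "in each of the pre-specified subgroups". It also gives the reporting format: "Data will be presented as odds ratios and 95% confidence intervals for categorical variables and as mean differences and 95% confidence intervals for continuous variables".

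The surrounding text sets the defaults. Under the analysis principles in section 12.2, "All analyses will be unadjusted unless otherwise specified" and "Subgroup analyses will be performed irrespective of treatment efficacy". Section 12.6 names the tests: "All between-group comparisons with continuous variables will be performed using Mann-Whitney U tests and Chi-square or Fisher's exact test for categorical variables". Section 12.4 makes every comparison other than the primary one secondary.

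No section mentions an interaction or heterogeneity test, and none names a subgroup, a cut-point or the number of subgroup factors. The subgroup paragraph reads as complete, so this does not look like text lost to redaction or PDF extraction.

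**The concern.** A subgroup analysis is usually done to learn whether the treatment effect varies with a patient characteristic. That is a comparison of two effects. The plan estimates each effect but never compares them. Mann-Whitney, Chi-square and Fisher's exact tests, used as section 12.6 describes, compare the two arms; applied within one subgroup level, they say nothing about the contrast between levels.

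The risk lies in interpretation. If one interval excludes no effect and the other includes it, a reader may conclude that the fastener helps one kind of patient and not another, although the true effect is the same and the split is chance.

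The missing list adds to this. Subgroups described as pre-specified but written down nowhere cannot be verified as such, and the number of looks is open.

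**Working it through.** **Inputs**

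- From section 12.1: difference 5 per 1,000 ventilator days, "a standard deviation of 15 per 1000 ventilator days", 80% power, two-sided alpha 0.05, 142 per arm, 500 planned, 5.6% dropout.
- From section 1.0: 1:1 allocation.
- Assumed, because no subgroup is named: one factor with two equal-sized levels and the same true difference of 5 in both.
- Assumed: normal-theory comparison of means, as in the sample size calculation. The plan's Mann-Whitney test would give somewhat different figures.

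**Step 1: the plan's own figure.** n per arm = 2 × [SD × (1.960 + 0.842) / difference]² = 2 × [15 × 2.802 / 5]² = 141.3, rounded up to 142. This matches section 12.1.

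**Step 2: sample sizes to show.** The total for 142 per arm is 284, and 284 / 0.944 is about 301, so the planned 500 does not follow from 142 per arm plus 5.6% dropout. I therefore show three sizes: 142; 500 × 0.944 / 2 = 236; and 500 / 2 = 250. Overall power on the plan's inputs is 80%, 95% and 96%.

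**Step 3: separate analyses.** With m = n/2 patients per arm in each level:

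- SE within a level = 15 × √(2/m)
- power within a level, p = Φ(5/SE − 1.960)
- probability that exactly one of the two levels is significant = 2p(1 − p)

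**Step 4: interaction test.** The SE of the difference between the two effects is √2 × the within-level SE. When the true effects are equal, the test rejects 5% of the time at any sample size. Power for a true difference of 5 between the two effects = Φ(5/SE − 1.960).

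| n per arm | m | SE within level | p | Exactly one level significant | SE of interaction | Power, interaction of 5 |
|---|---|---|---|---|---|---|
| 142 | 71 | 2.518 | 51% | 50% | 3.560 | 29% |
| 236 | 118 | 1.953 | 73% | 40% | 2.762 | 44% |
| 250 | 125 | 1.897 | 75% | 37% | 2.683 | 46% |

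For 80% power on an interaction of 5, n per arm = 8 × (15 × 2.802 / 5)², about 566.

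**Step 5: are there enough events for interaction models?** The documents give no ventilator days per patient; I assume 3 to 10. With 472 patients that is 1,416 to 4,720 ventilator days. At the 1.1 lip ulcers per 1,000 days of section 12.1, this gives about 1.6 to 5.2 ulcers in the whole trial. At the combined rate of 21.1 per 1,000 (dislodgement plus lip ulcers), it gives about 30 to 100 events. An interaction model on lip ulcers alone is not workable. One on the composite is thin but possible for a two-level factor.

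**The case against.** **The plan reports estimates and makes no subgroup claims.** Section 12.5 asks for odds ratios or mean differences with 95% confidence intervals, which is most of what a good subgroup display needs. A reader might infer that the plan will declare the device effective in one subgroup and not in another. It contains no such rule. This stands and softens the point, but a 95% interval that excludes no effect is commonly read as a significant result, and the tests in section 12.6 could produce subgroup p-values as well.

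**Subgroup results are already demoted.** Section 12.4 classes them as secondary. That stands too, but ranking them below the primary does not supply the missing comparison or name the subgroups.

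**The commitment to run subgroups whatever the overall result.** A reader might take "Subgroup analyses will be performed irrespective of treatment efficacy" as part of the problem. It is not: it prevents running them only after a convenient overall result, and interaction analyses would be run on the same basis.

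**Multiplicity.** It is tempting to add that ten subgroup tests with no true effect would give a 40% chance of at least one false positive (1 − 0.95¹⁰). The documents do not support that count, since no number of factors is given. Tests on different factors also reuse the same patients and are not independent. Nor do interaction tests remove multiplicity: five of them, treated as independent, would still give about 23% (1 − 0.95⁵). The argument for the test does not rest on this figure.

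**Interaction tests have low power.** True, as the table shows. An inconclusive interaction is then an accurate report of what the trial can say.

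**Conclusion.** The point holds as a low-cost improvement to a secondary analysis. As written, section 12.5 cannot show whether the treatment effect differs between subgroups, and its subgroups are called pre-specified without being listed.

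Under the stated assumptions, a contrast with one level significant and the other not would arise by chance 37% to 50% of the time although the effects are identical, against 5% per factor for an interaction test. A reader might take 50% as the expected figure. It is the maximum that 2p(1 − p) can reach, and it applies at 142 per arm; at the planned enrolment the figure is about 40% or 37%. Subgroups of unequal size, a different true effect or a rank test would change these percentages but not the conclusion about method, which rests on the text alone.

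**What to change.** In section 12.5, before outcome data are seen:

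- Keep the within-subgroup estimates and 95% confidence intervals. For each factor add one model with treatment, subgroup and their interaction, and report the interaction estimate, its 95% confidence interval and p-value.
- Name the effect scale, for example an odds ratio for the composite event. The Mann-Whitney analysis in section 12.4 states no effect measure to carry over.
- Apply the interaction models to the composite, not to sparse components such as lip ulcers alone. State which composite is meant, since section 1.0 includes facial skin tears where section 12.4 has VAP.
- List a few baseline factors with their levels. Reintubation is in the section 8.0 baseline list. Location of intubation is in the section 12.3 reporting list but not in section 8.0, so confirm that it is collected.
- Label the subgroup results exploratory.

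The cost is SAP wording and a few extra models, with no additional patients. The downside is the low interaction power shown in the working: most results will be inconclusive and should be reported as such.

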#### **12.6 Presentation of Statistics**

Continuous variables will be described as mean and standard deviation or median and 25th percentile – 75th percentile or bootstrapped 95% confidence intervals as appropriate. Categorical variables will be given as percentage and number. All between-group comparisons with continuous variables will be performed using Mann-Whitney U tests and Chi-square or Fisher's exact test for categorical variables

#### **13.0 Privacy/Confidentiality Issues**

At no time during the course of this study, its analysis, or its publication will patient identities be revealed in any manner. The minimum necessary data containing patient or provider identities will be collected. All patients will be assigned a unique study ID number for

Principal Investigator: [name], ACNP-BC

Study Title: Adhesive Versus Endotracheal Tube Fastener

Institution: Vanderbilt University Medical Center

Version Date: 3/21/2018

tracking. Data collected from the medical record will be entered into the secure online database REDCap. Hard copies of the data collection sheet completed at the time of the airway management event will be stored in a locked file cabinet in a locked room until after the completion of enrollment and data cleaning. Once data are verified and the database is locked, all hard copies of data collection forms will be destroyed. All data will be maintained in the secure online database REDCap until the time of study publication. At the time of publication, a de-identified version of the database will be generated.

#### **14.0 Follow-up and Record Retention**

Patients will be followed after enrollment for 28 days or until hospital discharge, whichever occurs first. Data collected from the medical record will be entered into the secure online database REDCap. Hard copies of the data collection sheet completed at the time of the airway management event will be stored in a locked room until after the completion of enrollment and data cleaning. Once data are verified and the database is locked, all hard copies of data collection forms will be destroyed. All data will be maintained in the secure online database REDCap until the time of study publication. At the time of publication, a de-identified version of the database will be generated.

